7 STUDY ASSESSMENTS AND TREATMENT SCHEDULE

Table 2 below lists all of the required assessments that should be performed at each study visit.

TABLE 2: STUDY ASSESSMENTS AND TREATMENT SCHEDULE

	Screen Screen			пероі	Cycles 2-6 ² After Cycle 6 ³							
Cycle = 28 days	*	Cycle 1 ¹				C2	С3	C4	C5	C6	q3 Cycles (C9, 12, etc.)	End of
Procedure\Days	-21-0	D1	D24	D8	D15			Day 1			Day 1	study
Informed consent	X											
Medical history	X											
Rai Staging	X											
ECOG Performance Status	X	X				X	X	X	X	X	X	Х
Physical Examination	X	X				X	X	X	Х	Х	X	X
Vital signs (pulse, BP, temp)	х	X	х	X	Х	X	X	х	х	х	х	х
BM aspirate/biopsy ⁵	Х											
12-lead EKG	Х											
Tumor evaluation ⁶	х	After the completion of cycles 2, 4 and 6 then after the completion of every 3 cycles if under treatment or every 3 months if in follow up										
Serology: HCV, HBV, CMV ⁷	х											
MRD8						For patients in PR or CR at response assessment intervals beginning at the Cycle 6 response assessment						
Hematology ⁹	X	X	X	X	X	X	X	X	X	X	X	Х
Serum Chemistry ⁸	X	X		Х	X	X	X	X	X	Х	X	X
PT/INR	X					X		X				
Serum Pregnancy Test ¹⁰	X											
Urinalysis	X											
Quantitative Immunoglobulin ¹¹		X			X		X			X		
β ₂ -microglobulin	X											
FISH Analysis ¹²	X											
Concomitant Medications	X	X	X	X	X	X	X	X	X	X	X	X
Adverse Event Evaluation ¹⁵	х	X	х	х	х	Х	Х	Х	Х	х	х	х
Treatment Schedule												
Ublituximab Dose		X16	X	X	X	X	X	X	X	X	X	

 $^{^{1}}$ Physical Exam, Vital Signs, ECOG PS, Hematology and Serum Chemistry visit days have +/- 3 day window

² Physical Exam, Vital Signs, ECOG PS, Hematology and Serum Chemistry visit days have +/- 7 day window

³ Physical Exam, Vital Signs, ECOG PS, Hematology and Serum Chemistry visit days have +/- 14 day window

⁴ Day 2 visit only required for patients randomized into Arm A.

⁵ Unilateral bone marrow aspirate and/or biopsy performed at investigator discretion in patients for whom assessment of extent of CLL involvement and bone marrow cellularity is important in determining eligibility. In addition, a post-baseline bone marrow biopsy should be completed to confirm potential CR by radiological assessment.

⁶ Scans for screening should be completed within 30 days prior to Day 1 of Cycle 1. Response tumor evaluations have a +/- 7 day window. Radiology assessment should include CT or MRI imaging of neck, chest, abdomen, and pelvis.

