12.5.2 ABNORMAL LABORATORY VALUES AND VITAL SIGNS

The reporting of abnormalities of vital signs as adverse events should be avoided. Abnormalities of vital signs should not be reported unless any criterion for an SAE is fulfilled, the vital signs abnormalities cause the patient to discontinue study treatment, or the investigator insists that the abnormality should be reported as an AE. Abnormal laboratory results should be noted in the eCRF as an adverse event if they are associated with an overdose, require or prolong inpatient hospitalization, or are otherwise considered clinically significant by the investigator. If an abnormal laboratory value or vital sign is associated with clinical signs and/or symptoms, the sign or symptom should be reported as an AE, and the associated laboratory value or vital sign should be considered additional information that must be collected in the relevant eCRF. If the laboratory abnormality is a sign of a disease or syndrome, only the diagnosis needs to be recorded on the SAE Report Form or AE eCRF.

Clinical Laboratory Results will be summarized. Summary statistics for actual values and for changes from baseline will be tabulated for laboratory results by scheduled visit. Patients with laboratory values outside of the normal reference range at any post-baseline assessment will be summarized, and graded per NCI CTCAE Version 4.0 when applicable. Patient incidence of abnormal laboratory results will be summarized by treatment group and maximum grade for each abnormal laboratory finding.

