³ Physical Exam, Vital Signs, ECOG PS, Hematology and Serum Chemistry visit days have +/- 14 day window

⁴ Day 2 visit only required for patients randomized into Arm A.

⁵ Unilateral bone marrow aspirate and/or biopsy performed at investigator discretion in patients for whom assessment of extent of CLL involvement and bone marrow cellularity is important in determining eligibility. In addition, a post-baseline bone marrow biopsy should be completed to confirm potential CR by radiological assessment.

⁶ Scans for screening should be completed within 30 days prior to Day 1 of Cycle 1. Response tumor evaluations have a +/- 7 day window. Radiology assessment should include CT or MRI imaging of neck, chest, abdomen, and pelvis.

7 Serum virology to include HBsAg, HBc antibody and CMV. If HBcAg, HBc antibody, HCV or CMV is positive, patients must be evaluated for the presence of

DNA/PCR

⁸ Peripheral Blood sample draw (See study manual for all central lab instructions. +/- 7 day window for MRD sample). For patients MRD negative by peripheral blood, a bone marrow sample should be completed to confirm MRD negativity.

⁹ Must be obtained prior to ublituximab administration if on a day of infusion.

 $^{^{10}}$ For women of child bearing potential, completed within 3 days prior to Day 1 of Cycle 1

¹¹ IgA, IgE, IgG, IgM

¹² For del(13q), del(11q), del(17p), and (12)trisomy, IgHV and P53 gene mutation status in peripheral blood. Central FISH analysis can be performed on UTX-IB-301 study or the TGTX-LAB-001 screening protocol.

¹⁵ If clinically significant adverse event or abnormal result is observed that is not resolved by the end-of treatment visit, continue to monitor and record until stabilization or resolution of event

¹⁶ Patients should receive up to 150 mg on Day 1 and 750 mg on Day 2. Collect a hematology panel prior to Day 2/Cycle 1 infusion.

Ibrutinib Dose	Days 1 – 28 (Daily)	
*Randomize Days -7 to 0		

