4.1 DEFINITION OF BASELINE

In general, the last observed measurement prior to or on the first administration of study treatment will be considered the baseline measurement.

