8.1.1.1 LOCAL LABORATORY ANALYSES

The following laboratory evaluations will be performed at a laboratory affiliated with the site:

• Hematologic profile will be performed at baseline and on Days 1, 2 (Arm A only for ublituximab), 8 & 15 of Cycle 1, Day 1 of Cycles 2-6, and every 3 cycles thereafter.

Hematologic Profile			
Hematocrit	Neutrophils	Platelet count	
Hemoglobin	Lymphocytes		
Erythrocyte count	Monocytes		
Absolute neutrophil count	Eosinophils		
Absolute leukocyte count	Basophils		

• Serum chemistry will be obtained at baseline and on Days 1, 8 & 15 of Cycle 1, Day 1 of Cycles 2-6, and every 3 cycles thereafter

Serum Chemistry				
Albumin	Creatinine	SGOT [AST]		
Alkaline phosphatase	Glucose	SGPT [ALT]		
Bicarbonate	LDH	Sodium		
BUN	Magnesium	Total bilirubin		
Calcium	Phosphorus	Total Protein		
Chloride	Potassium	Uric acid		

- Serum β-HCG test will be obtained within 3 days prior to the initiation of therapy for women of childbearing potential.
- Coagulation lab tests to include, PT, aPTT, and INR will be drawn at screening.
- Quantitative immunoglobulin (IgG, IgM, IgA, IgE) test will be obtained at pre-dose on Day 1 and Day 15 of Cycle 1, on Day 1 of Cycle 3 and Cycle 6.
- Urinalysis to be obtained at screening (dipstick for pH, protein, glucose, blood, nitrite, leukocytes.
- Beta2-microglobulin to be obtained at screening.
- Serum Virology at screening to include HBsAG, HBc antibody, HCV antibody, and CMV

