8.1.2 STATISTICAL ANALYSIS

Continuous laboratory test results will be summarized descriptively by study drug received for actual values and for changes from Cycle 1 Day 1. Visits to be summarized include all scheduled post-Cycle 1 Day 1 visits.

Shift from baseline tables for laboratory parameters will be presented. Categories will be based on CTCAE grade (where applicable) or by high/low flags (where CTCAE grades are not defined). Data will be analyzed at all post-Cycle 1 Day 1 visits, by worst grade post-Cycle 1 Day 1. Laboratory tests that have high and low abnormalities will be summarized separately for each direction (e.g., hypocalcemia and hypercalcemia).

Abnormalities in laboratory tests that the investigator considers clinically significant will be recorded and summarized as AEs.

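### Arm A's extra Cycle 1 Day 2 hematology draw enters the worst-grade tables and can modestly inflate its hematology abnormalities relative to Arm B

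*SAP*

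**What the plan says.** SAP 8.1.1.1 sets the draw schedule: "Hematologic profile will be performed at baseline and on Days 1, 2 (Arm A only for ublituximab), 8 & 15 of Cycle 1". Footnote 4 to Table 2 in Protocol Section 7, repeated in the SAP's Table 2, agrees: "Day 2 visit only required for patients randomized into Arm A". Footnote 16 fixes the timing of the panel: "Collect a hematology panel prior to Day 2/Cycle 1 infusion".

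SAP 4.1 defines baseline so that "the last observed measurement prior to or on the first administration of study treatment will be considered the baseline measurement". The first administration is on Cycle 1 Day 1, so the Day 2 panel is post-baseline.

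For the shift tables, SAP 8.1.2 states "Data will be analyzed at all post-Cycle 1 Day 1 visits, by worst grade post-Cycle 1 Day 1". Protocol 12.5.2 plans the matching incidence table: "Patient incidence of abnormal laboratory results will be summarized by treatment group and maximum grade for each abnormal laboratory finding". Neither document leaves Day 2 out, limits the tables to visits that both arms share, or allows for the number of draws.

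Chemistry differs. SAP 8.1.1.1 says "Serum chemistry will be obtained at baseline and on Days 1, 8 & 15 of Cycle 1", with no Day 2 draw in either arm.

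**The concern.** Worst grade is a maximum over the available draws. When one arm has an additional scheduled draw, its maximum is taken over a larger set. A short-lived abnormality on Day 2 is recorded in Arm A, whereas one in Arm B would have no scheduled draw to detect it.

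The extra draw also comes at a time when counts may be moving. Protocol 3.2.2 reports, for single-agent ublituximab, a fall of more than half in circulating lymphocytes with a median time to peripheral response of one day.

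Describing the safety of adding ublituximab is a secondary objective, and readers will judge cytopenias from these tables by arm. A worst-grade table does not itself show that the arms were observed unequally.

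**Working it through.** The documents state no figure on this point, so there is nothing to reproduce. The check counts draws and then asks how large the excess could be if the arms did not truly differ.

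**Step 1: scheduled hematology draws after Cycle 1 Day 1** (SAP 8.1.1.1 and Table 2, End of study not counted).
- Arm B through Cycle 6 Day 1: Days 8 and 15, plus Day 1 of Cycles 2 to 6, so 2 + 5 = 7. Arm A adds Day 2, so 8.
- Through Cycle 12 Day 1 (adding Cycles 9 and 12): 10 against 9.
- Through Cycle 24 Day 1 (adding Cycles 15, 18, 21 and 24): 14 against 13.

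**Step 2: independent draws with equal risk.** Let p be the chance of a given abnormal grade at any one draw, the same in both arms. The chance of at least one in k draws is 1 − (1 − p)^k, so the Arm A excess through Cycle 6 is p(1 − p)^7. The values of p are assumptions.

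| p | Arm A (8 draws) | Arm B (7 draws) | Excess (points) |
|---|---|---|---|
| 1% | 7.7% | 6.8% | 0.9 |
| 2% | 14.9% | 13.2% | 1.7 |
| 5% | 33.7% | 30.2% | 3.5 |
| 10% | 57.0% | 52.2% | 4.8 |

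The expression p(1 − p)^7 peaks at p = 1/8, where it is 0.125 × 0.875^7 = 0.125 × 0.393 = 0.049. Under these assumptions the excess therefore cannot exceed 4.9 points at any p. With about 60 patients per arm (approximately 120 randomized 1:1), that is at most about 3 patients.

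**Step 3: correlated draws.** Serial counts in one patient are not independent. With an exchangeable probit model and the same values of p, the excess through Cycle 6 is:
- latent correlation 0.5: 0.5 to 2.2 points;
- latent correlation 0.9: 0.1 to 0.6 points;
- abnormalities that always persist to a shared visit: 0.

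**Step 4: longer follow-up.** The planned tables run over all visits, and treatment continues until progression or toxicity. Through Cycle 24 with independent draws the excess is p(1 − p)^13: 0.9 points at 1%, 2.6 at 5% and 2.5 at 10%.

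**Step 5: restricting to shared visits.** Without Day 2, both arms have 7 scheduled draws through Cycle 6 Day 1 and 9 through Cycle 12 Day 1. Under equal risk the schedule-driven difference is 0.

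**The case against.** The strongest reply is that much of any Day 2 excess would be real. Only Arm A receives ublituximab and its corticosteroid premedication (Protocol synopsis and 8.1). A change in counts after that infusion is an effect of the Arm A regimen, which a safety table ought to show. This stands. It means that Day 2 values must not be dropped from the main Arm A table, where a Grade 3 or 4 value would otherwise be lost.

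A reader might go further and suppose that Day 2 carries a risk of, say, 10% to 20% against 5% at other visits. Through Cycle 12 with independent draws, that would add 0.10 × 0.95^9 = 6.3 points or 0.20 × 0.95^9 = 12.6 points, about 4 or 8 of 60 patients. The documents give no such rates, and an excess produced that way would be largely treatment effect, so it does not measure schedule bias.

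Other parts of the reply also stand:
- Persistence limits the artifact. In the earlier single-agent study in Protocol 3.2.2, median lymphocyte count fell from 46.6 to 1.5 × 10^9/L at month 1 and was still 1.4 and 2.0 at months 4 and 6, so depletion of that kind would also be seen at shared visits.
- Day 2 is already partly visible, because SAP 8.1.2 summarizes continuous results at each scheduled visit.
- SAP Section 7 has no pre-specified safety outcome and treats any formal comparison as post-hoc.
- Unequal time on treatment can also make the number of draws differ, and restricting to shared visits does not remove that.

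None of this removes the asymmetry. A pooled worst-grade table cannot separate a treatment effect from an additional look.

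**Conclusion.** The point holds as a modest, one-directional reporting artifact. Arm A has one more scheduled post-baseline hematology draw, and both documents take the worst grade over all visits without allowing for it. Under equal per-visit risk the excess through Cycle 6 is about 0 to 5 points. The upper end requires independent draws and a per-visit risk near 10%, and high correlation or persistence brings the excess close to 0. The per-visit risks and correlations are assumptions.

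A reader might infer that Arm A must show more abnormalities by construction. The schedule supports only the weaker statement that Arm A shows no fewer, all else equal: Day 2 counts only when it is the patient's sole worst value. A reader might also infer that a main safety comparison is compromised. The documents do not support that either: the tables are descriptive, chemistry is balanced, and no test or error rate is affected.

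**What to change.** In SAP 8.1.2:

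1. Keep the all-visit worst-grade and shift tables, so that no Day 2 toxicity is lost, and footnote that Arm A includes one additional scheduled hematology draw on Cycle 1 Day 2.
2. For the between-arm hematology comparison, add a worst-grade and shift table limited to visits scheduled in both arms: Cycle 1 Days 8 and 15, Day 1 of Cycles 2 to 6, every third cycle thereafter, and End of study.
3. Show graded Cycle 1 Day 2 hematology separately for Arm A.

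The table planned in Protocol 12.5.2 can carry the same footnote when it is produced. Chemistry tables need no change.

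This is a cheap improvement. It costs a few lines of SAP text and one or two extra tables, with no change to data collection or trial conduct. The downside is that acute Day 2 events are read apart from the common-visit comparison.

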8.2 VITAL SIGNS

8.2.1 VARIABLES

The following vital signs will be summarized:

- Blood pressure (systolic and diastolic, mmHg)
- Oral temperature (Celsius)
- Pulse rate (beats/min)
- Respiration rate (breaths/min)
- Body weight (kg)

8.2.2 STATISTICAL ANALYSIS

Summary tables of vital signs and change from baseline will be presented for all scheduled visits where vital signs were assessed. All recorded vital sign data will be listed.

8.2.3 PHYSICAL EXAM

Physical examination data will be presented in a data listing.

8.2.4 ECOG PERFORMANCE STATUS

ECOG Performance Status will be summarized as shift from baseline tables by visit using frequencies and percentages at all scheduled visits where performance status was assessed.

9 IDENTIFICATION AND SUMMARY OF PROTOCOL DEVIATIONS

Major protocol deviations from entry criteria and treatment compliance will be summarized as far as they can be extracted from numeric or coded study data.				

10 DATA QUALITY ASSURANCE

Accurate and reliable data collection will be ensured by verification and cross check of the CRFs against the investigator's records by the study monitor (source document verification) and by the maintenance of a drug-dispensing log by the investigator. Collected data will be entered into a computer database and subject to electronic and manual quality assurance procedures.

12 APPENDIX A - IMPUTATION RULES FOR MISSING DATA

Terminology in this appendix: first dose = first administration of any study treatment

The date of event (death/progression) is the documented date of event.

The missing date will be handled as follows:

What is	s missing in event date	Imputed value is
Year		
•	If month is missing or cannot be confirmed to be earlier than the month of last assessment	the year of last assessment
•	If, without considering year, the date of the event is confirmed to be earlier than the date of the last assessment (e.g., January vs November or May 15 vs May 1)	the year of last assessment+1
Month		
•	If year of the event is missing or is confirmed to be the same as the year of the last assessment	Month of the last assessment unless the day of death is earlier than the day of the last assessment (5th vs. 10th). In this case the month will be imputed as the month after the month of the last assessment
•	If year of the event is confirmed to be after the year of the last assessment	January
Day		1, unless the resulting imputed date is earlier than the last assessment date. In this case the imputed day is the day of the last assessment

Adverse Event

- If onset date is completely missing, onset date is set to date of first dose.
- If (year is present and month and day are missing) or (year and day are present and month is missing):
 - o If year = year of first dose, then set month and day to month and day of first dose.
 - o If year < year of first dose, then set month and day to December 31st.
 - o If year > year of first dose, then set month and day to January 1st.
- If month and year are present and day is missing:
 - If year=year of first dose and
 - ❖ if month = month of first dose then set day to day of first dose date.
 - ❖ if month < month of first dose then set day to last day of month.
 - ❖ if month > month of first dose then set day to 1st day of month.
 - o if year < year of first dose then set day to last day of month.
 - o if year > year of first dose then set day to 1st day of month.
- For all other cases, set onset date to date of first dose.

Concomitant Medications/Medical History

- If start date is completely missing, start date will not be imputed.
- If (year is present and month and day are missing) or (year and day are present and month is missing), set month and day to January 1.
- If year and month are present and day is missing, set day to 1st day of month.
- If end date is completely missing, end date will not be imputed.
- If (year is present and month and day are missing) or (year and day are present and month is missing), set month and day to December 31.
- If year and month are present and day is missing, set day to last day of the month.

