5.6 PRIOR AND CONCOMITANT MEDICATIONS

All medications recorded on the CRFs will be coded using the WHO or MedDRA dictionary. Prior and concomitant medications will be summarized by treatment arm in the ITT and Treated Population by anatomical therapeutic chemical (ATC) Class Level 4 and WHO Drug base substance preferred name.

Prior medications are defined as medications with stop dates occurring before the date of first administration of any study treatment component. Concomitant medications are defined as medications with start dates occurring on or after the date of first administration of any study treatment component and no more than 30 days after the last administration of any study treatment component. Medications with start and stop dates that bracket the date of first administration of any study treatment component will be summarized as both prior and concomitant medications.

For the purpose of summarizing prior and concomitant medications, incomplete medication start and stop dates will be imputed as detailed in Appendix A. Based on imputed start and stop dates, medications that clearly stopped prior to date of first administration of any study treatment component will be included in the prior medications table, and medications that clearly started on or after date of first administration of any study treatment component will be included in the concomitant medications table. All other medications will be included in both the prior and concomitant medications tables.

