6.1.2.5 PROGRESSION-FREE SURVIVAL

Progression-free survival is defined as the time from the date of randomization until the date of first documentation of definitive disease progression or date of death from any cause, whichever occurs first. Patients who die without a reported prior progression will be considered to have progressed on the day of their death. Patients who did not progress or are lost to follow-up will be censored at the day of their last tumor response assessment. If no baseline or post-baseline assessment is available, the patient will be censored at the date of randomization. If death or PD occurs after 2 or more consecutive missing tumor response assessments, censoring will occur at the date of the last response assessment prior to the missed assessments. The use of a new anticancer therapy prior to

the occurrence of PD will result in censoring at the date of last tumor response assessment prior to initiation of new therapy.

This variable will be analyzed using stratified log-rank test, and median PFS will be estimated via Kaplan-Meier methodology. PFS may not be formally analyzed at the time when the planned formal ORR analysis is conducted with approximately 120 patients who have had the opportunity to provide two efficacy assessments as it is expected that the majority of the patients from both treatment arms will not have progressed by the time of the primary ORR analysis (PFS may not be reliably estimated due to high censoring). Following the primary analysis of ORR, PFS may be analyzed at a later date. PFS will be analyzed using a stratified Cox regression model with treatment effect and stratification effect to estimate HR and 95% CI.

Censoring rules for PFS are summarized in Table 3.

TABLE 3: CENSORING RULES FOR PFS

Situation	Date of Progression or Censor	Censored/ Progressed
No baseline radiological tumor assessments	Randomization date	Censored
No post-baseline tumor assessments and no death reported before data cut-off	Randomization date	Censored
Disease progression	Date of progression	Progressed
No disease progression	Date of last tumor assessment	Censored
Treatment discontinuation for toxicity or other reasons with no disease progression per IRC	Date of last tumor assessment	Censored
Patient lost to follow-up without disease progression	Date of last tumor assessment	Censored
Death before first tumor assessment	Date of death	Progressed
Death between adequate tumor assessments	Date of death	Progressed

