Death or disease progression after ≥ 2 missed tumor assessments	Date of last tumor assessment before missed assessments or randomization date if no other tumor assessment in between	Censored
Withdrawal due to symptomatic deterioration without further tumor assessments	Date of last tumor assessment before discontinuation	Censored
Patient use of any anti-cancer therapy and/or surgery for curative intent.	Date of last tumor assessment prior to therapy or surgery, whichever occurs first	Censored
Note: Progression-free survival = date of even	t / censor – randomization date + 1	

Once the progression and survival dates are derived, PFS will be calculated as follows for patients with a PFS event:

PFS (days) = date of PD or death due to any case – randomization date + 1

(with censoring indicator = event)

For those patients who are censored for a PFS event:

[figure not shown]
PFS (days) = date of censoring – randomization date + 1

(with censoring indicator = censored)

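### The missing-year rule for death and progression dates in SAP Appendix A contradicts its own example, and its two rows overlap for same-month dates

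*SAP*

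**What the plan says.** Appendix A of the SAP handles death and progression dates by which component is missing. For a missing year there are two rows.

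- Row 1 assigns the year of the last assessment if the month is missing or "cannot be confirmed to be earlier than the month of last assessment".
- Row 2 assigns the following year. Leaving the year aside, it applies when the event's date is confirmed to be "earlier than the date of the last assessment (e.g., January vs November or May 15 vs May 1".

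The month rule below them gives its own example with the day of death first and the day of the last assessment second (5th against 10th).

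Two censoring rules depend on these dates.

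- SAP 6.1.2.5 and Table 3 censor PFS at the last assessment before the gap in the case of "Death or disease progression after ≥ 2 missed tumor assessments". Table 3 is introduced as the rules for PFS.
- SAP 6.1.2.5 also states that new anticancer therapy before "the occurrence of PD will result in censoring at the date of last tumor response assessment prior to initiation of new therapy". SAP 6.2 applies a similar new-therapy rule to both DOR and PFS.

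Protocol 11.9 says the SAP will give the imputation algorithms for missing dates of major efficacy parameters, and SAP 4.3 sends the reader to Appendix A. The appendix has no entry for the start of new anticancer therapy. Its only rule for a partial medication start is under Concomitant Medications/Medical History: "If year and month are present and day is missing, set day to 1st day of month", or January 1 if the month is missing too.

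**The concern.** A worked example in an imputation table is often what gets programmed. Here one of the two examples points the wrong way, and the two rows can give different years for the same record. A one-year error does more than shift a date. It can create an apparent run of missed scans and so change a PFS event into a censored observation at the last scan. In DOR it can lengthen a response by about a year. DOR is one of the three secondary outcomes in the SAP's Hochberg procedure.

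The new-therapy dates raise a related question. Whether a progression counts depends on the order of two dates, and the SAP does not say what to do when one of them is incomplete.

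**Working it through.** **Inputs.** The year rows, and the event-first order of the month-rule example, are from Appendix A. Cycles are 28 days (SAP 3.2). Scans follow cycles 2, 4 and 6, then every 3 cycles, or about every 3 months in follow-up (SAP 3.1). The intervals are therefore 2 × 28 = 56 days, 3 × 28 = 84 days, and about 91 days. The scan window is ±7 days (SAP Table 2). I take the appendix's last assessment to be the last tumor assessment, because the appendix does not define it.

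**Step 1: can one reading order reproduce both examples?** Row 2's condition adds 1 only if the event's month/day is earlier than the assessment's.

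| Pair and order | Row 2 condition gives | Row 1 gives | Printed example gives |
|---|---|---|---|
| January / November, event first | +1 | does not apply | +1 |
| May 15 / May 1, event first | +0 | +0 | +1 |
| May 15 / May 1, assessment first | +1 | +0 | +1 |
| January / November, assessment first | +0 | +0 | +1 |

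Event-first fits January/November and fails for May. Assessment-first fits May and fails for January/November. No single order reproduces both.

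**Step 2: effect of programming the May example as printed.** Last scan 1 May 2018, death on 15 May, year missing.

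- Condition as worded, and row 1: 15 May 2018 − 1 May 2018 = 14 days, with 0 missed assessments. The death is a PFS event.
- Example as printed: 15 May 2019 − 1 May 2018 = 365 + 14 = 379 days (380 if a leap day intervenes).
- Missed assessments = whole part of (379 − 7) / interval. This is 372/84 = 4.4, so 4; 372/91 = 4.1, so 4; 372/56 = 6.6, so 6.
- All are at least 2, so Table 3 censors PFS at 1 May 2018.
- For DOR, SAP 6.2 states no missed-assessment rule and counts death after stopping study drug as an event. The death stays an event, 379 − 14 = 365 days late.

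**Step 3: the overlap.** Last scan 15 May 2018, death on 1 May, year missing.

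- Row 1: May is not an earlier month than May, so the year is 2018 and the death falls 14 days before the scan. That is impossible for a death.
- Row 2: May 1 is earlier than May 15, so the year is 2019 and the death falls 365 − 14 = 351 days after the scan.
- No precedence is stated. The month and day rows of the same appendix do guard against a date before the last assessment. Row 1 of the year rule does not.

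**Step 4: after correction.** With the example reversed and row 1 limited to dates not earlier than the last assessment, the Step 2 record gives 14 days and a PFS event. The Step 3 record meets row 2 only.

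**Step 5: the new-therapy gap.** This is a what-if, not a stated rule. Suppose progression is on 10 June 2018, therapy truly starts on 20 June, and the day is missing. If the medication-summary rule were borrowed, the start would become 1 June, before progression. Censoring would fall at the previous scan, 84 days earlier on an 84-day schedule (18 March).

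In a 30-day month, with progression equally likely on any day and therapy L days later, the share reversed is (30 − L − 1)/30:

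- L = 7: 22/30 = 73%
- L = 14: 15/30 = 50%
- L = 21: 8/30 = 27%
- L = 28: 1/30 = 3%

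The lag is an assumption and dominates the answer.

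**The case against.** The best defence of the year rule is that the fault sits in a parenthesis. Both row 2's wording and row 1 give the correct year for a May 15 event after a May 1 scan, so a programmer who follows the text and ignores the example gets 14 days. That is fair for the example. It does not answer the overlap, which comes from the rows' own wording.

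The reach is also narrow. A month and day recorded without a year is unusual. Progression dates come from the independent committee's time point (SAP 6.2) and should be complete, so deaths are the main exposure. PFS carries limited inferential weight: it is outside the Hochberg set, Protocol 11.10.2.1.6 plans no formal test, and SAP 6.1.2.5 says it may not be formally analyzed at the ORR analysis. All of this stands and limits the size of the point.

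A reader might go further in three ways that the documents do not support.

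- One might infer that the SAP sets partial new-therapy starts to the earliest day and so reverses their order with progression. SAP 5.6 does define concomitant medications to include those begun "no more than 30 days after the last administration of any study treatment component", which makes the rule tempting to borrow. But 5.6 invokes the imputation for summarizing medications, and 6.1.2.5, Table 3 and 6.2 do not apply it to censoring. This is a gap.
- One might infer that the year error removes DOR events by the same route as PFS events. The missed-assessment rule is written for PFS only. A misdated progression could drop out of DOR through the separate 30-day rule in 6.2; a misdated death could not.
- One might put a number on the events lost. The documents give no event count, no share of partial dates and no lag to new therapy, so any count would be assumption.

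**Conclusion.** The missing-year rule is internally wrong and should be corrected. Its May example contradicts its condition, and its two rows give different years for a same-month event earlier than the last assessment. The size per affected record is large: 14 days becomes 379, with PFS changed from event to censored, or DOR for a death extended by about 365 days. The number of affected records is probably very small. That judgment assumes that missing years are rare and committee dates complete, since the documents give no counts. ORR does not use these dates.

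The absence of a rule for partial new-therapy start dates is a secondary point. It is a real omission, because the order of therapy and progression decides censoring for both PFS and DOR. Its effect cannot be sized from the documents.

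**What to change.** In Appendix A:

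1. Change the second example in row 2 to May 1 against May 15, event first, to match the other examples.
2. Let row 1 apply only when the month is missing or the known month/day is not earlier than that of the last assessment. The rows are then exclusive, and no imputed death precedes the last assessment.
3. State that the 1st-of-month/January 1 rule serves the medication summaries in 5.6 and is not used for new-therapy censoring. Pre-specify a rule for a partial start date of new anticancer therapy, and add a sensitivity analysis of PFS and DOR with the opposite ordering of therapy and progression.

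Item 3 leaves the choice of rule to the sponsor, because either ordering is one-sided: one drops true progressions, the other keeps events the plan means to censor. The sensitivity analysis shows whether the choice matters.

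The cost is a few lines of SAP text and programming, plus one extra run of the two analyses. It should be settled before database lock, since choosing between event and censoring afterwards would be data-dependent.
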